5.3.3.3 Time to First Achievement of PASI-50

As the PASI score is only collected at each study visit, the time to first occurrence of PASI-50 should be considered as interval-censored data. It is only known that the participant achieved PASI-50 at some point at or before the assessment at which it was first observed and after the previous assessment.

For participants who meet the criteria for PASI-50, the interval start and stop day for first achievement of PASI-50 will be defined as:

Interval start day = Study day of last PASI assessment before PASI-50 was first achieved +1

Interval end day = Study day of PASI assessment at which PASI-50 was first achieved

Participants who do not meet the criteria for PASI-50 during the Part A of the study will be right-censored at the last PASI assessment within 4 days of treatment discontinuation (for participants who did not complete the 16-week treatment period) or the last PASI assessment in Part A (for participants who did complete the 16-week treatment period). For the purposes of the analysis data set, the interval start and stop dates will be defined as:

Interval start day = Study day of last PASI assessment+1

Interval end day = missing

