5.3.3.4 Duration Endpoints

The following duration endpoints will be defined:

Duration of remission is defined as time from first achievement of PASI-100 to loss of PASI-100 or start of a new psoriasis treatment whichever occurs first.

Duration of treatment success is defined as time from first achievement of PASI-50 to loss of PASI-50 or start of a new psoriasis treatment whichever occurs first.

Duration of therapeutic effect is defined as time from cessation of study treatment until increase of PASI to 50% of maximum improvement from baseline or start of a new psoriasis treatment whichever occurs first. Maximum improvement from baseline is a participant's lowest post-baseline PASI score. Increase of PASI to 50% of maximum improvement from baseline can only occur at a visit after the visit where maximum improvement from baseline occurred. Any participant who showed no improvement in PASI score from baseline up to end of treatment will not have duration of therapeutic effect calculated. Any participant who showed an improvement prior to end of treatment and whose end of treatment PASI score had already gone above 50% of maximum improvement from baseline will have duration of therapeutic effect equal to zero.

As the PASI score is only collected at each study visit, the duration endpoints should be considered as interval-censored data. Although an exact date of start of new psoriasis treatment will be collected, it is only known that the participant achieved and lost PASI-100/50 status, or achieved an increase of PASI to 50% of maximum improvement from baseline, at some point at or before the assessment at which it was first observed and after the previous assessment.

Duration should be calculated as:

Duration = End Day - Start Day

For duration of remission and duration of treatment success:

Start Day = Study day of PASI assessment at which PASI-100 or PASI-50, respectively, was first achieved

End Day = Study day of PASI assessment at which PASI-100 or PASI-50, respectively, was first lost, or start of new psoriasis treatment whichever occurs first

For duration of therapeutic effect, duration should be calculated as:

Start Day = Study day of end of study treatment

End Day = Study day of PASI assessment at which increase of PASI to 50% of maximum improvement from baseline first occurred, or start of new psoriasis treatment, whichever occurs first

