If a participant does not meet the Start Day criteria relevant to a particular duration endpoint at any time during the study the endpoint will not be calculated.

If a participant has not met the End Day criteria relevant to a particular duration endpoint by the final study visit the last PASI assessment in Part A or Part B will be used as the End Day in the calculations above.

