8.6 Treatment Compliance

Treatment compliance will be summarised for each 8-week treatment period and for the whole 16-week treatment period.

Summary statistics (n, mean, SD, median and range) will be produced together with the number and percentage of participants within each of the categories defined in [Section 5.3.2.2](#). Percentages will use the number of participants who started the relevant treatment period as the denominator.

Data from the dosing log and the calculated treatment compliance in each treatment period will also be listed.

9 Efficacy Analyses

In addition to the inferential analyses described below, descriptive statistics will be provided to summarize all efficacy endpoints by treatment group.

For categorical variables, summary tabulations of frequency and percentage of participants within each category will be presented.

For continuous variables and duration endpoints, the number of participants, mean, median, standard deviation (SD), minimum, and maximum values will be presented.

For time to event endpoints, the number of participants with the event, the number of participants censored will be presented together with Kaplan-Meier estimates of time to 25% and 50% (median) of participants with event. Kaplan-Meier curves of time to event will also be presented.

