9.5.6 Partial Relapse, Relapse and Rebound

The following endpoints will be summarised by treatment group and visit in the

- Week 16 responders population:
 - Cumulative incidence of partial relapse at Weeks 20, 24, 28, and 40
 - Cumulative incidence of complete relapse at Weeks 20, 24, 28, and 40
- mITT population:
 - Cumulative incidence of rebound at Weeks 20, 24, 28, and 40

These summary tables will include the number of participants meeting the criteria for the endpoint, and the number of participants 'at risk' of meeting the criteria (the denominator for the cumulative incidence i.e. excluding any participants with a missing status for that endpoint).

For each endpoint, the cumulative incidences for each treatment group will be plotted against time (Week 20 to Week 40) as bars (with an 'error bar' for the corresponding 95% CI).

No inferential analysis of relapse or rebound will be carried out.

Table 6 Intercurrent Event Strategies for Partial Relapse, Relapse and Rebound Endpoints

Endpoint	Intercurrent event	Strategy to account for intercurrent event
Partial Relapse and (Complete) Relapse	Starting a new psoriasis treatment	Composite Starting a new psoriasis treatment is part of the endpoint definition

Endpoint	Intercurrent event	Strategy to account for intercurrent event
Rebound	Starting a new psoriasis treatment	
While in the period following cessation of study treatment, without taking a new psoriasis treatment (analogous to While on treatment)
 
Rebound status will be considered missing from 4 days after the day a new psoriasis treatment is started, onwards, and will not be counted in the denominator during calculation of cumulative incidences

Note that, according to the study design, starting a new psoriasis treatment (synonymous with study treatment failure) should result in a subject completing a PASI questionnaire at an unscheduled Follow-up (Part A)/Early Withdrawal (Part B) visit within 72 hours and then being withdrawn from the study. The above strategies for dealing with the intercurrent event of starting a new psoriasis treatment are included to cover the possibility of a protocol deviation occurring whereby a participant is not withdrawn from the study within 72 hours following the start of a new psoriasis treatment, and to clarify the estimand for rebound.

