Once a participant has met the criteria for partial relapse, relapse or rebound (see [Section 5.3.3.2](#)) they will be counted as having met those criteria at the current (if a PASI criterion at Week 20 or later) or next, and all subsequent, scheduled visits where these endpoints are analysed (Week 20, 24, 28, and 40).

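### Part B: responses never lost are averaged as if they had ended, Visit 14 is labelled Week 40 but dated at Week 31, and Week 40 rebound status needs a one-line rule

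*SAP*

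**What the plan says.** **Durations (exploratory).** SAP 5.3.3.4 states that "the duration endpoints should be considered as interval-censored data". It then calculates End Day minus Start Day and, where the ending criterion was never met, "the last PASI assessment in Part A or Part B will be used as the End Day". SAP Section 9 puts these endpoints with the continuous variables: "For continuous variables and duration endpoints, the number of participants, mean, median, standard deviation (SD), minimum, and maximum values will be presented". Its next paragraph describes the other route: "For time to event endpoints, the number of participants with the event, the number of participants censored will be presented together with Kaplan-Meier estimates". That route is not applied to durations. In SAP 5.3.3.3 the same kind of incomplete time is handled differently: "Participants who do not meet the criteria for PASI-50 during the Part A of the study will be right-censored at the last PASI assessment".

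**Who is followed.** Under Protocol Table 6-2, footnotes b and c, Visits 12 and 13 (Weeks 24 and 28) are for everyone except treatment failures and rebounders. Visit 14 is only for Week 16 responders who have not relapsed by Week 28.

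**Visit 14.** Table 6-2 gives Week 40, 6 months after end of treatment, Day 218, window 204-232. Protocol 3.1 gives follow-up to Week 40, 24 weeks after dosing ends, and a maximum participation of 44 weeks.

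**Rebound (secondary, descriptive).** SAP 9.5.6 reports cumulative incidence in the mITT population at Weeks 20, 24, 28 and 40. The tables show the number meeting the criteria and the number at risk, defined as "the denominator for the cumulative incidence i.e. excluding any participants with a missing status for that endpoint". Table 6 adds: "Rebound status will be considered missing from 4 days after the day a new psoriasis treatment is started, onwards". The section closes with a carry-forward rule: "Once a participant has met the criteria for partial relapse, relapse or rebound", the participant counts at that or the next scheduled visit and at all later ones.

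**The concern.** A response still present at the last PASI has a known minimum duration but no known end. Entering the minimum as the duration makes the mean depend on when follow-up stops. It also shrinks differences between doses, because the longest-lasting responses are cut most. The reader cannot correct for this, because no summary shows how many responses were ongoing. For therapeutic effect the cut-off also depends on outcome: non-responders stop at Week 28, while responders who have not relapsed continue to Visit 14.

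The date of Visit 14 sets where that last cut-off falls. If sites follow the day and window entries, Part B ends about nine weeks earlier than the week label says. If they follow the label, the visit is outside its window.

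For rebound, SAP 9.5.6 does not say whether a participant who is rebound-free at Week 28 and not scheduled for Visit 14 is missing or free of rebound at Week 40.

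**Working it through.** **1. Visit days.** Tables 6-1 and 6-2 use day = 7 × week + 1. This reproduces the other 11 post-baseline visits: Weeks 1, 2, 3, 4, 6, 8, 12, 16, 20, 24 and 28 give Days 8, 15, 22, 29, 43, 57, 85, 113, 141, 169 and 197. Visit 14 does not fit:
- Week 40: 7 × 40 + 1 = Day 281. The table gives Day 218, a difference of 281 − 218 = 63 days.
- Day 218: (218 − 1)/7 = Week 31. Window: (204 − 1)/7 = Week 29 to (232 − 1)/7 = Week 33.
- Gap from Visit 13: 218 − 197 = 21 days as dated, or 281 − 197 = 84 days as labelled.
- Visit 13's window (190-204) and Visit 14's window (204-232) share Day 204.
- SAP 7.7 reports data by nominal visit. A visit on Day 218 is therefore reported as Week 40. A visit on Day 281 is also reported as Week 40, but is logged as a deviation, 281 − 232 = 49 days outside the window.

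**2. Effect of the End Day rule.** The documents give no loss rates, so these are assumptions: PASI-50 first seen at Week 16, exponential loss with true median M weeks, everyone followed for C weeks, exact loss times. Then:
- share unlost = 2^(−C/M)
- true mean = M/ln 2
- planned mean = (M/ln 2) × (1 − 2^(−C/M))
- planned median = the smaller of M and C

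| M | True mean | C = 24 (Day 281): unlost, mean, median | C = 15 (Day 218) | C = 12 (Day 197) |
|---|---|---|---|---|
| 12 | 17.3 | 25%, 13.0, 12 | 42%, 10.0, 12 | 50%, 8.7, 12 |
| 24 | 34.6 | 50%, 17.3, 24 | 65%, 12.2, 15 | 71%, 10.1, 12 |
| 52 | 75.0 | 73%, 20.5, 24 | 82%, 13.6, 15 | 85%, 11.1, 12 |

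Two arms with M = 12 and M = 24 differ in true mean by 34.6 − 17.3 = 17.3 weeks. Their planned means differ by 17.3 − 13.0 = 4.3 weeks at C = 24. The median is right in every cell with up to half unlost, and becomes the follow-up limit in the others.

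**3. Visit dating.** Losses are dated at the visit where they are first seen, which works in the other direction. With visits at 4, 8, 12 and 24 weeks after Week 16, the planned mean is 4 + 4S(4) + 4S(8) + 12S(12), where S(t) = 2^(−t/M):
- M = 24: 4 + 4(0.891) + 4(0.794) + 12(0.707) = 19.2, against a true 34.6.
- M = 12: 4 + 4(0.794) + 4(0.630) + 12(0.5) = 15.7, against 17.3.
- M = 6: 4 + 4(0.630) + 4(0.397) + 12(0.25) = 11.1, against 6/ln 2 = 8.7.

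The End Day rule always pulls the mean down. For short responses, late dating can outweigh it.

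**4. Therapeutic effect.** The clock starts at the end of treatment, Day 112 for completers (SAP 5.3.4.2). A non-responder whose effect has not ended is cut at (197 − 112)/7 = 12.1 weeks. A non-relapsed responder is cut at (281 − 112)/7 = 24.1 weeks, or (218 − 112)/7 = 15.1 weeks if seen on Day 218.

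**5. Rebound wording.** SAP 5.3.3.2 has a comma before the 3-month limit, so the limit covers both the PASI criterion and new pustular or erythrodermic disease. Protocol 6.1.1 has no comma, so the limit may cover only the second. On the SAP reading the limit falls at about Day 112 + 91 = Day 203. Visit 13 is on Day 197, 85 days after Day 112, so status is essentially settled at Week 28.

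**The case against.** **The median.** A reader might infer that the planned median is unreliable throughout. The documents do not support that. With common follow-up the plain median equals the Kaplan-Meier median whenever fewer than half are unlost. The damage is to the mean, and to the median only when about half or more are unlost, when participants leave early, or at the Week 28 limit for therapeutic effect.

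**Status of the endpoints.** Durations are exploratory, no inference is planned on them, and both documents name the endpoint as a mean. All true, and it limits the weight of the point. It does not make an ongoing response complete, and the SAP itself calls the data interval-censored.

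**Rebound inflation.** A reader might infer that Week 40 rebound is inflated several-fold because most participants leave the denominator. For example, 3 rebounds in an arm of 50 with 10 rebound-free attenders would read 3/13 = 23.1% instead of 3/50 = 6.0%. That requires counting an unscheduled visit as missing status. The SAP's definition essentially settles status at Week 28, and keeping a settled status is not imputation. The planned tables also show the number at risk, so a fall in the denominator would be visible, and no inference is planned. What stands is that the rule is unwritten and the two documents word the limit differently.

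**Rebounders who start treatment.** A reader might also infer that Table 6 removes established rebounders once they start a new treatment. The closing paragraph of SAP 9.5.6 explicitly keeps them counted. The note under Table 6 says its strategies cover participants who were not withdrawn as planned, and clarify the rebound estimand. One sentence on the order of the rules is enough.

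**Visit 14.** The protocol text repeatedly says Week 40, and out-of-window data are still analysed. That does not remove the contradiction within Table 6-2.

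**Conclusion.** The point holds for the durations and for Table 6-2, and should be fixed. Rebound needs only a minor clarification.

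The End Day rule lowers mean durations. Under the assumed exponential loss and follow-up to Week 40, a quarter to nearly three quarters of responses are unlost for true medians of 12 to 52 weeks. Planned means are then 13.0 to 20.5 weeks, against true means of 17.3 to 75.0. These are illustrations, not predictions: the true loss rates are unknown, and visit dating offsets part of the effect when responses are short. That unlost responses are counted as ended and not reported separately follows from the text without any assumption.

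Table 6-2 contradicts itself by 63 days for Visit 14. The documents do not settle which entry governs, so none is preferred here. The primary analysis is unaffected by any of the three parts.

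**What to change.** **Durations.**
- In SAP 5.3.3.4, right-censor unlost responses at the last PASI, as 5.3.3.3 does.
- In Section 9, move durations to the time-to-event paragraph. Report the number censored and a Kaplan-Meier or interval-censored median and quartiles, with not reached where it applies.
- For remission and treatment success, state the first-observed visit as the origin. An interval-censored estimate also deals with the late dating of losses.
- For therapeutic effect, keep the existing exclusion and zero-duration rules. Either limit the estimate to Week 28, or report Week 16 responders and non-responders separately beyond it. A single Kaplan-Meier curve past Week 28 would apply the experience of non-relapsed responders to everyone.
- Record the change in SAP Table 8, since the endpoints are named as means.

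**Table 6-2.** The week, month, day and window entries for Visit 14, and the shared Day 204, must be reconciled.

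**Rebound.**
- Reconcile the 3-month wording between Protocol 6.1.1 and SAP 5.3.3.2.
- If the limit covers both criteria, state that participants rebound-free at Week 28 and not scheduled for Visit 14 keep that status at Week 40. If not, report rebound in the full mITT set to Week 28 only.
- State that the carry-forward rule applies to established rebounders ahead of Table 6.

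**Cost.** SAP wording, a Table 8 entry, reprogramming of three duration tables (14.4.2.18, 14.2.2.20, 14.4.2.21), a check of the rebound table and figure (both 14.4.2.17), and a correction to the protocol schedule. No new data. Some medians may be not reached, and the planned mean is replaced.

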5.3.3.5 Physician Global Assessment

The physician will give a score on the participant's psoriasis disease for each of induration (thickness), erythema (redness) and scaling on a scale of 0 to 5. Further information on the PGA is provided in [Section 17](#).

The PGA score will be calculated as the average of the three scores, rounded to the closest whole number.

PGA score will be calculated within the eCOA system and taken directly from the supplied data prior to the rounding being applied.

The rounded PGA value will be used in the calculation of the PGA*BSA variable and will also be used in any summaries and listings of the PGA data.

5.3.3.6 Percent of Body Surface Area Involvement

The percent of BSA involvement will be estimated for each participant, where 1% is approximately the area of the participant's handprint.

BSA-75 response is defined by at least a 75% reduction from Baseline in the BSA.

5.3.3.7 Lesion Severity Score

The lesion of interest, selected at the screening visit, will be scored for redness, induration (thickness) and scaling using a five-point scale:

- 0=None
- 1=Slight
- 2=Moderate
- 3=Severe
- 4=Very severe

The LSS is the sum of the redness, induration and scaling scores at each visit. The LSS will not be calculated unless all three sub-scores are non-missing.

All assessments must be performed throughout the study on the same lesion of interest as identified at Screening. If a different lesion is scored, compared to the Screening visit, then the LSS will be considered missing.

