During the screening period, participants will be advised to monitor their psoriasis symptoms and remain on a stable regimen of topical emollients and low-dose topical corticosteroid medications (if they are already taking any). Participants will be asked to withhold the application of any emollients or moisturizers on the day of any site visit until after all study assessments have been performed. As part of the screening, PASI, BSA involvement, and PGA scores will be measured (inclusion criterion #4, Section 4.1.1).

Participants meeting eligibility criteria at screening will return to the study site on Day 1. The PASI, BSA involvement, and PGA scores must be available to reconfirm eligibility prior to randomization and administration of the first dose of study drug on Day 1 (Visit 2).

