6.1.2 Lesion Severity Score

The LSS is used to score the severity of psoriasis plaques (Patel and Tsui 2011). The dimensions of scaling, erythema, and plaque elevation are each scored on a scale from 0 to 4, and the total LSS is the numerical sum of the 3-dimensional scores observed at a single study visit.

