6.4.3 Pharmacodynamics and Biomarkers

Procedures for sample collection, processing, storage, and shipment will be detailed in the study specific laboratory manual. Biomarkers are exploratory endpoints and analytical results for biomarkers will not be included in the CSR. They will be reported separately from the CSR.

Digital photographs should be taken of up to 6 lesion sites that have a lesion area ideally greater than 2 cm by 2 cm at baseline. The same locations photographed at baseline should be followed throughout the study for each participant. Procedural details for digital photography will be provided in the specific user manual.

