4.2 Endpoints

The primary efficacy endpoint for the study is:

- Percentage change in PASI score from baseline at Week 16.

The secondary efficacy endpoints for the study are:

- Percentage change in PASI score from baseline at Weeks 4, 8 and 12.
- Absolute change from baseline in PASI score at Weeks 4, 8, 12 and 16.
- Achievement of PASI-50 at Weeks 4, 8, 12 and 16.
- Time to first achievement of PASI-50.
- Achievement of PASI-75, PASI-90 and PASI-100 at Week 16.
- Achievement of PGA of 0 or 1 with a ≥ 2 -point improvement from baseline at Week 16.
- Achievement of PGA of 0 at Week 16.
- Percentage change from baseline in PGA*BSA at Weeks 4, 8, 12, and 16.
- Absolute change from baseline in PGA*BSA at Weeks 4, 8, 12, and 16.
- Percentage change from baseline in LSS at Weeks 4, 8, 12, and 16.
- Absolute change from baseline in LSS at Weeks 4, 8, 12, and 16.
- Percentage change from baseline in DLQI score at Weeks 4, 8, 12, and 16.
- Absolute change from baseline in DLQI score at Weeks 4, 8, 12, and 16.
- Percentage change from baseline in mNAPSI total score at Weeks 4, 8, 12, and 16.
- Absolute change from baseline in mNAPSI total score at Weeks 4, 8, 12, and 16.
- Cumulative incidence of partial relapse at Weeks 20, 24, 28, and 40.
- Cumulative incidence of complete relapse at Weeks 20, 24, 28, and 40.
- Cumulative incidence of rebound at Weeks 20, 24, 28, and 40.

Exploratory efficacy endpoints are:

- Achievement of PASI-50, PASI-75, PASI-90, and PASI-100 at Weeks 4, 8, and 12.
- Achievement of PGA of 0 or 1 with a ≥ 2 -point improvement at Weeks 4, 8, and 12.
- Achievement of PGA of 0 at Weeks 4, 8, and 12.
- Achievement of PGA of 0 or 1 at Weeks 4, 8, 12, and 16.
- Percentage change from baseline in BSA at Weeks 4, 8, 12, and 16.
- Absolute change from baseline in BSA at Weeks 4, 8, 12, and 16.
- Achievement of BSA<3% and BSA-75 at Weeks 4, 8, 12, and 16.
- Absolute change from baseline in PSI quality of life total and itch scores at Weeks 12 and 16.
- Percentage change from baseline in PSI quality of life total and itch scores at Weeks 12 and 16.
- Absolute change from baseline in Pain and Fatigue scores at Weeks 4, 8, 12, and 16.
- Percentage change from baseline in Pain and Fatigue scores at Weeks 4, 8, 12, and 16.
- Absolute change from baseline in fasting blood glucose and fasting lipid panel at Weeks 8 and 16.
- Mean duration of remission in participants who achieve PASI-100.

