5.3.1.2 Baseline

The last non-missing value collected before first study dose will be taken as the baseline measurement for all parameters. If data is collected on Day 1 without an associated time being provided, it will be assumed to be pre-dose. Efficacy data collected using the electronic clinical outcome assessment (eCOA) device on the same day as the first dose of study medication will also be assumed to be pre-dose data and can be used for the baseline assessment, regardless of whether the time indicates if it was before or after the time of first dose.

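### The LSS validity rule in SAP 5.3.3.7 checks against a Screening lesion for which the protocol describes no selection step; it should check against the Baseline lesion

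*SAP*

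**What the plan says.** SAP 5.3.3.7 refers to Screening three times. It fixes the lesion there: "The lesion of interest, selected at the screening visit, will be scored for redness, induration (thickness) and scaling using a five-point scale". It then requires the same lesion at every visit: "All assessments must be performed throughout the study on the same lesion of interest as identified at Screening". It ends with the rule for departures: "If a different lesion is scored, compared to the Screening visit, then the LSS will be considered missing".

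The protocol does not describe that arrangement:

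- **Table 6-1 (Part A).** The LSS row is blank at Screening. The first LSS is at Baseline (Visit 2), followed by Weeks 1, 2, 4, 8, 12, 16 and 20. Table 6-2 adds Weeks 24, 28 and 40 and the early withdrawal visit.
- **Section 6, screening text after Table 6-2.** "As part of the screening, PASI, BSA involvement, and PGA scores will be measured". Neither the LSS nor a target lesion is mentioned.
- **Section 6.1.2.** "The LSS is used to score the severity of psoriasis plaques". The section gives the three dimensions and their sum, but names no target lesion and no time for choosing one.
- **Section 6.4.3.** The only lesion tracking in the protocol is photography, which starts at Baseline: "The same locations photographed at baseline should be followed throughout the study for each participant".

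SAP Table 8, which lists departures from the protocol, has no entry for the Screening lesion.

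On the analysis side, SAP 5.3.1.2 says "The last non-missing value collected before first study dose will be taken as the baseline measurement for all parameters". SAP 4.2 lists "Absolute change from baseline in LSS at Weeks 4, 8, 12, and 16" as a secondary endpoint, together with the percentage change at the same weeks.

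**The concern.** A change from Baseline in a single-lesion score is interpretable when the same lesion is scored at both ends. The SAP applies a different test: whether each scored lesion equals one chosen at an earlier visit (Day -28 to Day -7), where no LSS is scheduled. A series can fail that test and still be sound for its endpoint.

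When the Baseline score fails, the loss is complete. No earlier LSS is scheduled that could take its place under the SAP's baseline definition, so the participant drops out of both the absolute and the percentage change analyses. The Week 20 and Part B changes go as well.

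The SAP itself gives weight to consistency with Baseline. In 5.3.3.8 it explains that a wrongly asked DLQI question was left uncorrected so that later visits would not be compared with a different questionnaire at Baseline. The LSS rule does not follow that reasoning.

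**Working it through.** The plan gives no figure to reproduce here. The check has three steps.

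**1. Schedule.** Reading Table 6-1 across its 11 visit columns, the LSS row has no mark at Screening and 8 marks in all (Baseline and Weeks 1, 2, 4, 8, 12, 16, 20). The BSA/PGA/PASI row directly above has 9, including Screening, so the blank is not a fault of table extraction. From Baseline to Week 16 there are 7 scheduled scores, hence 7 − 1 = 6 changes from Baseline. Four of these (Weeks 4, 8, 12, 16) are named endpoints. Weeks 1 and 2 enter the repeated-measures model, because SAP 9.5.2 analyses the LSS in the manner of the primary endpoint.

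**2. What each rule keeps.** Let S, B and V be the lesions at Screening, at Baseline and at a later visit.

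- Screening anchor (SAP 5.3.3.7): the change at V is kept only if B = S and V = S.
- Baseline anchor: the change at V is kept only if V = B.

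If B = S and V = S, then V = B. Every change that survives the Screening anchor therefore survives the Baseline anchor. The reverse fails when V = B but B ≠ S: the change compares one lesion with itself, and only the Baseline anchor keeps it. Neither rule ever compares two different lesions.

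**3. Counts to Week 16** (7 scores, 6 changes).

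| Lesion pattern | Screening anchor: scores, changes kept | Baseline anchor: scores, changes kept |
|---|---|---|
| Every visit on the Screening lesion | 7 of 7, 6 of 6 | 7 of 7, 6 of 6 |
| Every visit on one other lesion | 0 of 7, 0 of 6 | 7 of 7, 6 of 6 |
| Only Week 8 on another lesion | 6 of 7, 5 of 6 | 6 of 7, 5 of 6 |
| Only Baseline on another lesion | 6 of 7, 0 of 6 | 1 of 7, 0 of 6 |

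For the endpoints, which are changes, the anchors differ only in the second row. In the last row the Baseline anchor keeps fewer individual scores (1 against 6), but no change can be calculated under either rule.

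**The case against.** The strongest reply is that selecting a lesion and scoring it are separate acts. The SAP says the lesion is selected at Screening, and the selected lesion can be scored for the first time at Baseline. A blank Screening cell in Table 6-1 does not contradict that. The rule compares which lesion was scored, not one score with another, and it acts only when a difference is found.

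This stands, and it rules out a stronger reading that someone might take from the blank cell: that the rule has nothing to match against, or that no LSS value could pass it. The documents do not support either. Without a Screening record no difference could be shown, and on the wording nothing would be voided.

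Three further points have weight:

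- **Recording.** The selection may be captured outside the protocol. Section 6 defers site detail to user manuals, and Section 8.1 has investigator assessments entered on electronic devices. The documents do not settle this either way.
- **Frequency.** No mismatch rate is given, so any head count of lost participants would be a guess.
- **Purpose.** Choosing the lesion before the day of randomization is a reasonable design, since it limits choice on that day. But the voiding rule is not needed to keep changes on a single lesion, because a Baseline check does that too. A departure from the selected lesion can be reported without deleting data.

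A Baseline anchor also needs lesion identity to be recorded at each LSS visit, which the documents do not show. The present rule needs the same information and, in addition, the Screening record.

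**Conclusion.** The point holds as a minor one. SAP 5.3.3.7 makes LSS validity depend on a Screening selection that the protocol does not describe, and it tests against the wrong visit for a change-from-Baseline endpoint.

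The size is conditional. A participant whose lesion is consistent from Baseline but differs from the Screening lesion loses all 6 changes to Week 16, including all four endpoint weeks, in both LSS endpoints. A participant whose lesions agree throughout loses nothing. How many fall in the first group is unknown. It would be wrong to infer that LSS data are deleted in general.

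The consequence is confined to the LSS. Protocol 7.6.2 treats secondary results as descriptive, and the primary PASI endpoint and the sample size are unaffected. The conclusion assumes that lesion identity is recorded at each LSS visit, so that a mismatch can be detected at all.

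**What to change.** Replace all three Screening references in SAP 5.3.3.7. Suggested content: the lesion of interest is the lesion scored at Baseline (Visit 2); later assessments are to be made on that lesion; a post-baseline LSS is set to missing only if the lesion scored differs from the Baseline lesion.

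If a lesion was also noted at Screening, list any Screening/Baseline mismatch with the protocol deviations (SAP 8.2) and keep the scores. Before finalising the text, confirm where lesion identity is held in the eCRF or the electronic assessment data.

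The cost is a rewording of three sentences in one section and one derivation rule. No new analysis is needed, and no new data provided lesion identity is already recorded. No change from Baseline that the present rule keeps would be lost.
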